5.4 Treatment of Outliers in Pharmacokinetic Analysis

Four outlier exclusion criteria which will be identified following PK analysis are addressed below.

5.4.1 Exclusion and Remedy for Plasma Concentration at each Time Point

MediBeacon developed the analytical methodology for MB-102 concentration determination in plasma. This method was shown to be very robust and much simpler than the usual analytical methods employed for iohexol determination in plasma samples. In the Pilot 2 Group 1 study, a rigorous method transfer and technician training program resulted in exceptional agreement between agent concentration in plasma samples measured at the sponsor lab and the third-party bioanalytical lab. The data was published in the peer-reviewed journal "Analytical Methods" (Shieh et. al. 2018²). However, when processing the Pilot 2 Group 2 samples, obvious errors in sample concentration were randomly observed. All indications pointed to lack of carefulness on the technician doing the work at the third-party bioanalytical lab.

Thus to ensure accuracy, it is necessary to implement a check on the bioanalytical lab that is performing the plasma agent concentration measurements. The plasma concentration vs time data generated by the third party bioanalytical lab is crucial to the clinical study endpoint. We have instituted further training on

² J. J. Shieh, I.R. Riley, R.B. Dorshow, Clinical analysis and quantitation of MB-102, a novel fluorescence tracer agent, in human plasma Royal Society of Chemistry, Anal. Methods, 2018, 10, 2376

Statistical Analysis Plan		Page 16 of 29
MediBeacon Inc.	An Open Label, Multi-Center, Safety and Pharmacokinetic Bridging Study of MB-102 (Relmapirazin) and the Use of the MediBeacon [®] Transdermal GFR Measurement System using the TGFR Reusable Sensor with Disposable Adhesive Ring in Normal and Renal Compromised Subjects for the Evaluation of Kidney Function	Ver 4.0

our analytical technique at the bioanalytical laboratory and have instituted written protocols covering the entire analysis procedure.

A review of all plots of such data both in linear space and semi-log space will be performed prior to the GFR calculation. An example of data in semi-log space is in **Figure 1**; red circles are the measured concentrations from a subject with normal kidney function, the blue line is the two-compartment pharmacokinetic fit.

Figure 1 Plasma concentration as a function of time for a subject with normal renal function

Should a data point be observed that is 20% off the fit line, this may be an indication of an issue with the sample or with sample preparation. Thus, for any plasma sample value that is greater than 20% off the fit line, a re-analysis of agent concentration will be performed in that sample. The request will be for re-analysis in triplicate (3 new PK analyses of the timepoint), and the average value for concentration from the triplicate run will be used for that time point in the calculation of plasma GFR. If WinNonLin default parameters are not able to provide a pharmacokinetic result, then the full set of PK timepoints for that subject will be re-analyzed in triplicate and the means used in the final analysis.

Statistical Analysis Plan		Page 17 of 29
MediBeacon Inc.	An Open Label, Multi-Center, Safety and Pharmacokinetic Bridging Study of MB-102 (Relmapirazin) and the Use of the MediBeacon [®] Transdermal GFR Measurement System using the TGFR Reusable Sensor with Disposable Adhesive Ring in Normal and Renal Compromised Subjects for the Evaluation of Kidney Function	Ver 4.0

Any quantifiable pre-dose concentration value will be considered anomalous and set to missing for the PK analysis, which will then be subsequently set to 0 by default in Phoenix WinNonlin.

It is anticipated that this exclusion criteria will seldom need to be employed due to our training program and written protocols at the third-party bioanalytical lab.

5.4.2 Exclusion Based on Subject Dosing Errors

In the initial implementation of the Pilot 2 Group 1, the site staff was not properly determining the amount dosed due to weighing errors of the agent-filled dosing syringe. The error in measured dose translated to error in GFR since:

GFR = Dose / AUC

where AUC is the area under the curve in the plasma concentration of MB-102 vs time plot. We subsequently implemented a strict weighing protocol to accurately determine the amount of administered dose, which has been followed for all subsequent studies, with the weighing protocol monitored by company staff at each study to prevent weighing errors of the dose.

In the 100-201 clinical study, which will be performed at up to 5 clinical sites, the clinical site staff will be expected to perform subject dosing error-free.. Written protocols will be provided to minimize dosing errors. However, as a check on dosing at the clinical sites, exclusion criteria based on the calculation of GFR from the standard two-compartment pharmacokinetic model and the indexed GFR will be implemented.

MB-102 plasma GFR is deduced using the MB-102 concentration vs time data and dose in the standard two-compartment pharmacokinetic model. We will use the most current version of WinNonlin for this task. The derived GFR is directly dependent on the input dose amount. This pharmacokinetic model also outputs many other parameters including the volume of distribution V_d . The derived V_d is also directly dependent on the input dose amount.

In the clinical setting, GFR is indexed to body surface area (BSA) using one of several formulas, all of which use the subject's height and weight. In fact, GFR indexed by BSA is how nephrologists stage kidney disease. The symbol $nGFR_{BSA}$ will be used for this indexing. Like non-indexed GFR, the GFR_{BSA} determination is also directly dependent on dose.

GFR can also be indexed by V_d . The symbol $nGFR_{Vd}$ will be used for this indexing. Because both the derived GFR and V_d are directly dependent on the input dose amount, indexing makes $nGFR_{Vd}$ independent of dose.

Statistical Analysis Plan		Page 18 of 29
MediBeacon Inc.	An Open Label, Multi-Center, Safety and Pharmacokinetic Bridging Study of MB-102 (Relmapirazin) and the Use of the MediBeacon [®] Transdermal GFR Measurement System using the TGFR Reusable Sensor with Disposable Adhesive Ring in Normal and Renal Compromised Subjects for the Evaluation of Kidney Function	Ver 4.0

Due to the dependence of $nGFR_{BSA}$ on dose amount and independence of $nGFR_{Vd}$ on dose amount, comparison of these two values reveals errors in dosing. An example is in **Figure 2** shown below from some of our clinical data obtained in the device optimization studies.

Figure 2: Plasma GFR indexing comparison

The y-axis is $nGFR_{BSA}$ and the x-axis is $nGFR_{Vd}$. Two of the 67 subjects are seen to be obvious outliers in a plot of $nGFR_{BSA}$ vs. $nGFR_{Vd}$. The conclusion is that a major dosing error has occurred for these two subjects.

It is anticipated that this exclusion criteria will seldom need to be employed due to our training program and written protocols at the clinical sites.

Statistical Analysis Plan		Page 19 of 29
MediBeacon Inc.	An Open Label, Multi-Center, Safety and Pharmacokinetic Bridging Study of MB-102 (Relmapirazin) and the Use of the MediBeacon [®] Transdermal GFR Measurement System using the TGFR Reusable Sensor with Disposable Adhesive Ring in Normal and Renal Compromised Subjects for the Evaluation of Kidney Function	Ver 4.0

5.4.3 Exclusion Based on Small Dosing Errors and/or Extravasations

MediBeacon have found that plasma determined nGFR may also be affected by more subtle issues. These include small dosing errors and/or small extravasations of the MB-102 dose.

For example, after deleting the two extreme outliers in **Figure 2**, and correcting for a small linear trend in the absolute difference between $nGFR_{BSA}$ and $nGFR_{Vd}$ for the remaining subjects, the root mean square (RMS) percent error of the difference of the two indices was computed in 20 mL/min wide $nGFR_{Vd}$ subject bins, as shown in the **Figure 3**:

Figure 3: RMS percent error of nGFR_{BSA} - nGFR_{Vd} as a function of nGFR_{Vd}.

Subjects were grouped into 20 mL/min wide bins according to $nGFR_{Vd}$. Error bars represent \pm the standard error within each binned group of subjects.

Statistical Analysis Plan		Page 20 of 29
MediBeacon Inc.	An Open Label, Multi-Center, Safety and Pharmacokinetic Bridging Study of MB-102 (Relmapirazin) and the Use of the MediBeacon [®] Transdermal GFR Measurement System using the TGFR Reusable Sensor with Disposable Adhesive Ring in Normal and Renal Compromised Subjects for the Evaluation of Kidney Function	Ver 4.0

The resulting RMS percent error is seen to be independent of $nGFR_{Vd}$ with a combined value of 13% across all subjects.

Choosing two times the RMS percent error as a threshold limit for outlier detection (since it is similar to the standard deviation) results in identification of four additional outlier subjects, as shown in the **Figure 4** below.

Figure 4: RMS percent error for $nGFR_{BSA}$ - $nGFR_{Vd}$ as a function of $nGFR_{Vd}$. Dashed lines are outlier thresholds

Summary: Two nGFR indexing calculations, $nGFR_{BSA}$ and $nGFR_{Vd}$, will be performed for all subjects in the 100-201 study. Any subject nGFR data that is an obvious outlier as described in section 2 above, and

Statistical Analysis Plan		Page 21 of 29
MediBeacon Inc.	An Open Label, Multi-Center, Safety and Pharmacokinetic Bridging Study of MB-102 (Relmapirazin) and the Use of the MediBeacon [®] Transdermal GFR Measurement System using the TGFR Reusable Sensor with Disposable Adhesive Ring in Normal and Renal Compromised Subjects for the Evaluation of Kidney Function	Ver 4.0

any subject nGFR that is outside the threshold boundary as described in **Figure 4** will be eliminated before applying the remaining nGFR data to the evaluation of the tGFR endpoint criteria.

It is anticipated that this exclusion criteria will need to be seldom employed due to implementation of a rigorous training program and written protocols at the clinical sites. However, MediBeacon has historically seen evidence of these minor deviations and need to ensure this is not occurring in our 100-201 clinical study data set.

5.4.4 Exclusion Based on Body Size

Body surface area calculation for subjects at the extremes of body size are problematic. This issue has been widely discussed and a good summary is in Redlarski et al 2016³. Thus, any subjects with nGFR_{BSA} > 120 mL/min/1.73m² will be excluded from the tGFR vs nGFR_{BSA} dataset comparison. Note that clinically this is not relevant as these are highly normal subjects with respect to kidney function.

It is anticipated that this exclusion criteria will seldom be employed due to the enrollment exclusion criteria that excludes subjects with an $eGFR > 120 \text{ mL/min/1.73m}^2$ per the CKD-EPI equation.

5.5 Presentation of Pharmacokinetic Data

All PK concentrations and parameters will be listed. As each subject will have a unique GFR measurement, summary statistics are not applicable in this analysis.

Individual figures will be provided for plasma PK concentrations. All figures will be produced on both linear-linear and logarithmic- linear scales with data and the two-compartment fit.

6 Transdermal Derived GFR Data

The transdermal-derived GFR data (tGFR) is obtained directly from the MediBeacon Transdermal GFR Measurement System (TGFR) for each subject. This tGFR value is compared to the subject's nGFR_{BSA} for the study endpoint determination.

³ G. Redlarski, A. Palkowski, M. Krawczuk, Body surface area formulae: an alarming ambiguity, Nature Scientific Reports 21Jun2016

Statistical Analysis Plan		Page 22 of 29
MediBeacon Inc.	An Open Label, Multi-Center, Safety and Pharmacokinetic Bridging Study of MB-102 (Relmapirazin) and the Use of the MediBeacon [®] Transdermal GFR Measurement System using the TGFR Reusable Sensor with Disposable Adhesive Ring in Normal and Renal Compromised Subjects for the Evaluation of Kidney Function	Ver 4.0

7 Analysis of Safety

All TEAEs reported during the study will be reviewed and adequately reported to comply with applicable regulations. All reportable TEAEs will be assessed by the investigator who will determine whether the event is related to MB-102 or related to the study device, and whether the event meets any of the criteria for seriousness. A serious adverse event (SAE) is any AE from this study that results in one of the following outcomes:

- led to death;
- led to serious deterioration in the health or the subject, that either resulted in:
 - 1. A life threatening illness or injury, or
 - 2. A permanent impairment of a body structure or a body function, or
 - 3. In-patient or prolonged hospitalization, or
 - 4. Medical or surgical intervention to prevent life-threatening illness or injury or permanent impairment to a body structure or a body function;
- led to fetal distress, fetal death or congenital abnormality or birth defect.

Significant findings that were noted to be present at or prior to dosing must be included in the relevant medical history page of the eCRF. Significant new findings that begin or worsen after dosing must be recorded on the AE page of the eCRF. Subjects should be followed until the event is resolved or stabilized. AEs are collected from the time of initial sensor placement until the completion of the follow-up visit.

All reported TEAEs, including unanticipated adverse device effects (UADE), and serious adverse events (SAE) will be summarized for all enrolled subjects. The overall numbers and percentages of subjects who experienced any TEAEs will be presented. In addition to the TEAEs, description of all TEAEs, including description/term of the symptom event (underlying diagnosis), the date of first occurrence and date of resolution (if applicable), classification of serious or not serious, severity, causal relationship, action taken, and event outcome will be listed. TEAEs will also be summarized at the subject level by system organ class and preferred term, and at the event level by system organ class/preferred term and severity and by system organ class/ preferred term and relationship to treatment.

In addition to the events reported as AEs, the parameters of clinical laboratory tests including clinical chemistry, hematology, urinalysis and coagulation parameters will be summarized using the descriptive

Statistical Analysis Plan		Page 23 of 29
MediBeacon Inc.	An Open Label, Multi-Center, Safety and Pharmacokinetic Bridging Study of MB-102 (Relmapirazin) and the Use of the MediBeacon [®] Transdermal GFR Measurement System using the TGFR Reusable Sensor with Disposable Adhesive Ring in Normal and Renal Compromised Subjects for the Evaluation of Kidney Function	Ver 4.0

statistics. Clinical laboratory analytes are presented in **Table 1**. More information on descriptive statistics is presented in **Section 8.6**.

ECG data will be listed. Concomitant medications, coded using the World Health Organization (WHO) drug dictionary, administered within 3 days prior to MB-102 dose administration and through the follow-up study visit will be also listed. Furthermore, concomitant non-drug therapies will be listed.

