9.6 Safety Analyses

Safety of MB-102 will be evaluated through treatment emergent adverse events (TEAEs), where treatment emergence is defined with respect to the first dose of MB-102.

Safety of the MediBeacon[®] Transdermal GFR Measurement System will be evaluated through TEAEs, where treatment emergence is defined with respect to the start time of Transdermal GFR Measurement System use (placement of the sensor on the skin).

Additional safety variables include physical examinations, clinical laboratory assessments, ECGs, and concomitant medication use.

All safety analyses will be done for subjects receiving a single dose of MB-102.

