9.6.2 Physical Examinations/Limited Physical Assessments

The results of physical examinations will be collected as adverse events if clinically significant or as medical history (if observations are noted prior to TGFR start). Physical exam data will not be listed.

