3.3 Safety Evaluation

Safety of MB-102 will be evaluated through treatment emergent adverse events (TEAEs), where treatment emergence is defined with respect to the first administration of MB-102.

Safety of the MediBeacon® Transdermal GFR Measurement System will be evaluated through TEAEs, where treatment emergence is defined with respect to the start time of device use. Additional safety variables include physical examinations, clinical laboratory assessments, ECGs, and concomitant medication use. All clinically significant findings in physical examinations, clinical laboratory assessments and ECGs will be reported as an AE or as medical history (if observations are noted prior to dose administration).

Statistical Analysis Plan		Page 12 of 29
MediBeacon Inc.	An Open Label, Multi-Center, Safety and Pharmacokinetic Bridging Study of MB-102 (Relmapirazin) and the Use of the MediBeacon [®] Transdermal GFR Measurement System using the TGFR Reusable Sensor with Disposable Adhesive Ring in Normal and Renal Compromised Subjects for the Evaluation of Kidney Function	Ver 4.0

4 Analysis of Primary Endpoint

The primary endpoint is the performance measure of P30 for transdermal-derived GFR with respect to the plasma-derived indexed GFR, with a 95% confidence interval. The performance goal is 85%. Success for the study will be that the lower limit of the 95% CI is greater than 85%.

The primary endpoint will be calculated for subjects enrolled into the Validation 2 and 3 (if applicable) cohorts only. The Run-in cohort and Validation 1 cohort enrollment were performed to provide final tuning data and used for software updates.

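### SAP 7 and Protocol 7.1.2 split medical history from AEs at dosing, but AE collection and device TEAEs start at sensor placement, so a sensor reaction before the injection may be misfiled

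*SAP*

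**What the plan says.** One paragraph of SAP 7 (Analysis of Safety) contains both sides of the conflict. It first directs: "Significant findings that were noted to be present at or prior to dosing must be included in the relevant medical history page of the eCRF". It continues: "Significant new findings that begin or worsen after dosing must be recorded on the AE page of the eCRF". It ends: "AEs are collected from the time of initial sensor placement until the completion of the follow-up visit". Protocol 7.1.2 has the same three sentences.

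Other places bear on the same boundary:

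- **Device treatment-emergence.** In SAP 3.3, "treatment emergence is defined with respect to the start time of device use". Protocol 9.6 says what that start is: "placement of the sensor on the skin".
- **Examination, laboratory and ECG findings.** SAP 3.3 treats clinically significant ones "as medical history (if observations are noted prior to dose administration".
- **Examination findings in the protocol.** Protocol 9.6.2 treats them "as medical history (if observations are noted prior to TGFR start". Protocol 7.1.2.8, on the same examinations, uses dosing.
- **Start of AE collection.** Protocol Table 2 note m, and the dosing-day lists in Protocol 6.5 and SAP 2.4, all place it at sensor attachment, before the injection.

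SAP 1 lets the SAP override the protocol where the two differ.

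**The concern.** The sensor is on the skin before MB-102 is given. A finding that starts in that interval is, by one rule, medical history, and by another, an adverse event that is treatment-emergent for the device. The precedence clause in SAP 1 does not settle it, because the SAP disagrees with itself.

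The history rule is mandatory and names the eCRF page, so a site following it literally would put a pre-injection skin reaction where the TEAE tables cannot find it. Two sites could also record the same reaction differently.

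Device safety is part of a stated objective. Protocol 3.3 attributes device-related events to the adhesive materials, and Protocol 8.2 ties sensor events to the way the sensor is fixed to the skin. The disposable adhesive ring is part of the configuration under test. The interval can also lengthen: under Protocol 5.5.1 and 7.1.2.5.1, a sensor displaced before dosing may be re-applied and baseline restarted, which means a further adhesive application and a chance to see the skin.

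**Working it through.** The plan gives no figure to reproduce. The check sets the rules side by side and then sizes the interval.

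**1. Where does a reaction first seen between sensor placement and injection go?**

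| Place | Applies to | Moment used | Destination |
|---|---|---|---|
| SAP 7 and Protocol 7.1.2, history and AE-page rules | significant findings | dosing | medical history, unless it worsens after dosing |
| SAP 7 and Protocol 7.1.2, AE collection rule | AEs | sensor placement | AE page |
| Protocol Table 2 note m, Protocol 6.5, SAP 2.4 | AEs | sensor placement or attachment | AE page |
| SAP 3.3 and Protocol 9.6 | device TEAEs | start of device use, i.e. sensor placement | device TEAE |
| Protocol 7.1.2.8 | examination findings | dosing | medical history, unless it worsens after dosing |
| SAP 3.3 | examination, laboratory and ECG findings | dose administration | medical history |
| Protocol 9.6.2 | examination findings | TGFR start | AE |

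The first two rows stand in the same paragraph and cannot both be followed.

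**2. Length of the interval.** Protocol Table 2 note g requires at least 15 minutes of sensor time before dosing. Protocol 6.5 puts baseline acquisition at about 20–30 minutes.

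**3. Share of wear time.** Share = pre-dose minutes / (pre-dose minutes + post-dose minutes). I assume wear for the full 720 minutes after dosing in Stratum 1 and 1440 minutes in Stratum 2.

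- Stratum 1: 20/740 = 2.7% to 30/750 = 4.0% (15/735 = 2.0% at the minimum).
- Stratum 2: 20/1460 = 1.4% to 30/1470 = 2.0% (15/1455 = 1.0% at the minimum).

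The upper Stratum 1 total of 750 minutes matches the 12.5 hours in Protocol 5.5. The shares rise if the sensor is removed early once a tGFR is reported, or if baseline is restarted.

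**4. Expected device events.** Protocol 8.1 reports device-related AEs in 7 Pilot 2 subjects, out of 234 exposed: 7/234 = 3.0%. For the 240 subjects who may be enrolled, 240 × 7/234 = 7.2.

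**5. Expected events in the interval, if onset is uniform over wear.**

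- Lowest usual share for everyone: 7.2 × 1.4% = 0.10.
- Highest usual share for everyone: 7.2 × 4.0% = 0.29.
- With half the subjects in each stratum: 3.6 × 2.7% + 3.6 × 1.4% = 0.15, to 3.6 × 4.0% + 3.6 × 2.0% = 0.22.

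So the figure is about 0.1–0.3 events in the whole trial.

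**6. Direction.** The history rule can move a device event off the AE page. Nothing in it moves a pre-existing finding onto that page. Any misfiling therefore runs towards fewer device events.

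**The case against.** The best defence is that every statement about when AE collection begins points to sensor placement: SAP 7 itself, Protocol 7.1.2, Table 2 note m, Protocol 6.5 and SAP 2.4. A site that reads these together would record a pre-injection sensor reaction as an AE. If the reaction worsens after dosing, the disputed rule itself puts it on the AE page. This stands, and it limits the claim. A reader might infer that such reactions are never counted, or that the device result is biased downward as a matter of rule. The documents do not support that. They show two conflicting instructions, so misfiling is possible but not established.

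SAP 3.3 is also narrower than it may look. Its cut-off covers examination, laboratory and ECG findings, not everything seen before dosing. Protocol 6.5 lists those assessments ahead of sensor attachment and bars other procedures during acquisition. For scheduled assessments the cut-offs in SAP 3.3 and Protocol 9.6.2 will therefore normally agree, and that difference is mostly one of wording.

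The exposed cases are few. A reaction beneath an undisturbed ring would probably be seen only at removal, after dosing. That leaves mainly a re-applied sensor, a visible reaction at the cord clip, or a symptom reported during baseline. The rule also applies only to significant findings. Study success rests on P30 alone, so no trial conclusion depends on this.

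None of this removes the contradiction in SAP 7 and Protocol 7.1.2.

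**Conclusion.** The point holds as an internal contradiction in a mandatory recording rule. A sensor, ring or clip reaction that appears between placement and injection and does not worsen afterwards may be filed as history and be missing from the device TEAE summary.

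The likely size is about 0.1–0.3 events in 240 subjects. That rests on two assumptions. The Pilot 2 rate must carry over, although Protocol 3.3 says Groups 1 and 2 were measured at two locations with prototype devices. Onset must also be uniform over wear, with full wear time and no restarted baseline.

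Two stronger readings should be avoided. With about 7 device events expected, one misfiled event would be 1/7 = 14% of the total, but that figure presupposes a misfiled event and is not an expected bias. Nor are adhesive reactions the only device-related events described: Protocol 8.1 attributes Pilot 1B headaches to the strap for a forehead sensor placement since discontinued. Adhesive reactions are the main such event, not the only one.

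The correction is still worth making. The rule departs from the trial's own device TEAE definition, its error runs in one direction, and the change is cheap.

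**What to change.** In SAP 7, SAP 3.3, Protocol 7.1.2 and Protocol 7.1.2.8, replace dosing with sensor placement (start of device use) as the boundary between medical history and the AE page. State that findings which begin or worsen after sensor placement go on the AE page. Keep the dose only as the origin for MB-102 treatment-emergence. This agrees with Table 2 note m, Protocol 9.6 and Protocol 9.6.2, which need no change. Protocol 7.1.2.8 must be included, or the dosing cut-off survives there.

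Skin irritation from hair clipping, which Protocol 7.1.2.11 sends to medical history, can stay there where it arises before the sensor is placed.

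The cost is wording in four sections and an eCRF completion note. If recording is already complete, a check of dosing-day medical-history entries with onset after sensor placement would serve the same purpose. The downside is that a few more device AEs may be reported.
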